### Exploratory outcomes

- A. Exploratory efficacy outcomes

- a. Clinically oriented

We will track the time from VGB load to resolution of PASE, time from VGB load to start of anesthetic wean, total duration of anesthetics for PASE treatment, the overall number of ASDs required for status epilepticus resolution, and the changes in neuron specific enolase (**NSE**), glial fibrillary acidic protein (**GFAP**), neurofilament light chains (**NfL**), tau and ubiquitin C-terminal hydrolase L1 (**UCH-L1**) overtime as a potential indirect metric of neuroprotection since higher neuronal injury burden is associated with elevated NSE, GFAP and NfL levels.

- b. Physician-reported

We will record Epidemiology-based Mortality Score in Status Epilepticus (**EMSE**) during index hospitalization to track disease severity. We will record the following outcomes at discharge, 6 months: modified Rankin Scale (**mRS**), Glasgow Outcome Scale- Extended (**GOS-E**), Glasgow- Pittsburgh Cerebral Performance Categories Scale original (**CPC**) and extended (**CPC-E**) in person visits. In case subjects cannot attend in person visits, a structured questionnaire will be employed for telephone assessments (**t-mRS**, **t-CPC**). Cognitive function will be assessed by Montreal Cognitive Assessment (**MoCA**).

- c. Length-of-stay

We will track total duration of anesthetic infusion for status epilepticus treatment, duration of mechanical ventilation, and ICU length-of-stay.

- d. Patient-reported

We will evaluate self-perceived functional outcomes with the 36-Item Short-Form Health Survey (**SF-36**) according to the Core Outcome Set for Cardiac Arrest (**COSCA**) initiative recommendations on the use of outcome measures of health-related quality of life (**HRQOL**).

B. Exploratory safety outcomes

a. Retinopathy

Concentric visual defects have been reported with chronic use of VGB. As such, we will be detecting rates of retinopathy on vision loss screening via Goldmann perimetry upon regain of consciousness during index hospitalization (earliest time-point during which subject is able to cooperate with testing), ICU discharge and 6 months. In addition, long-term visual screening at 6 months will include the Visual Function Questionnaire 25 (**VFQ-25**). We do not expect to observe visual field restrictions with a single load of VGB as visual toxicity correlates with high doses and prolonged therapy. Concentric visual defects with chronic use of VGB may be related to a decrease in taurine levels. We will monitor taurine levels at baseline, 72 hours, and 7 days post-VGB administration. We anticipate that a single load of VGB would not lead to a statistically significant reduction in taurine levels.

b. MRI brain

Prolonged VGB therapy has also been associated with reversible MRI changes in the basal ganglia, thalamus, cerebellum, and brainstem. Unconscious CA survivors undergo brain MRI between 2- and 7-days post-CA for neuroprognostic purposes as a standard of care. We will note the proportion of subjects with MRI changes in the VGB cohort.

C. Exploratory pharmacologic outcomes

a. Pharmacodynamics (**PD**) – ASD interactions.

b. VGB may reduce or increase serum levels of ASDs. We will monitor daily levels of antiseizure medications that are co-administered with VGB for 3 days to characterize these potential drug-drug interactions and ensure optimal dosing.

### Rationale for chosen outcomes

The phase IIa study is a feasibility study and is not powered to address efficacy or safety. We will collect these metrics and track percent of missing data and the time for completion to inform which clinical variables pertaining to efficacy and safety will become primary and secondary clinical outcomes in subsequent study phases.

The explicit purpose of this feasibility study is to deliver the drug within 48 hours of PASE onset and have measurable levels by 3-12 hours post-load in addition to completing visual screening. The reported bioavailability of VGB is 100%, with a wide volume of distribution, minimal binding to blood proteins and elimination mainly through renal clearance[42]. While plasma concentrations of VGB do not correlate with its effectiveness[42], they confirm successful absorption of this drug. Renal impairment is common after CA[66] and creatinine clearance influences VGB elimination[62]. Further, several other factors may affect VGB absorption in the post-CA period. Thus, we will follow serial VGB levels to characterize enteric absorption and clearance in this setting. Furthermore, given the potential for drug-drug interactions among ASDs, we will be monitoring other ASD levels. For example, up to a 20% reduction in total phenytoin plasma levels can be seen with co-administration of VGB[42, 67, 68], while up to a 10% increase in carbamazepine levels has been observed with co-administration of VGB[42].

Most landmark clinical trials with VGB did not include critically ill subjects. However, a recent trial evaluating the potential neuroprotective effects of VGB in severe traumatic brain injury demonstrated adequate absorption and elevated cerebral GABA levels as determined by microdialysis [53, 54]. Our study follows a design used in other studies, measuring serial VGB levels at baseline, 1, 3, and 12 hours following

VGB administration[53]; the addition of 0-, 0.5-, 1-, 2-, 3-, 6-, 12-, 24-, 48-, 72- and 168-hour (7 days) level measurements is aimed at accurately describing absorption, confirming clearance of the drug, and confirming the reported lack of correlation of drug levels with a sustained clinical effect. A pre-dose sample allows for confirmation that VGB is not already present in the study subjects and no interference in the quantification method.

Variation in anesthetic infusion weaning practices may confound the interpretation of successful wean from anesthetics. Further, anesthetics may be given to patients for other reasons than PASE treatment such as to maintain tolerability of mechanical ventilation and TTM. Thus, we chose to examine multiple secondary outcomes that could more accurately reflect the therapeutic effect of VGB and track the indication for maintaining anesthetic infusion rates daily. All the endpoints are objective and will be assessed by a blinded investigator to the timing of VGB administration.

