### Primary outcome

#### A. Primary feasibility outcome – enrollment and drug delivery

We will primarily be looking at the ability to deliver VGB in PASE subjects; the target will be administering 4,500mg (or dose adjusted in moderate and severe impairment) of VGB enterally within **48 hours of PASE onset** in ≥ 80% of enrolled subjects. Given the lack of well-established alternative treatments in this deadly disease, we anticipate 60-75% enrollment of eligible subjects, and will therefore be tracking the ratio between eligible and enrolled subjects, consent rates, and reasons for decline in study participation.

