#### B. Primary feasibility outcome – visual screening

We will obtain serial taurine levels during ICU stay and Goldmann perimetry testing in the subjects are able to cooperate at 6 months follow up. Our goal is to achieve 90% completion rate for taurine levels, and have reliable visual field perimetry in ≥ 80% of survivors that regain consciousness following index hospitalization.

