### Secondary outcomes

- A. Secondary feasibility outcome – PASE detection and ultra-early drug delivery
  - a. We will track the proportion of subjects in whom PASE was present upon connection to EEG (onset misses) to explore alternatives to allow prompt EEG monitoring following ROSC.
  - b. We will also track the proportion of enrolled subjects who received a VGB load within 12 and 24 hours of PASE onset to explore the possibility of ultra-early administration of VGB in subsequent phases, as the internalization of GABAA receptors (a key mechanism of treatment refractoriness) is time-dependent[65].

- B. Secondary pharmacologic outcome: PK – elimination

By analyzing serial VGB levels, we will characterize drug elimination. We anticipate undetectable VGB levels in all subjects by 7 days regardless of their renal function. Subjects with normal renal function will have undetectable VGB levels by 72 hours, and those with creatinine clearance less than 30 mL/min will have detectable VGB levels at 72 hours.

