## 6. Trial design

Phase IIa: This is a feasibility, single center, open-label pilot, with blinded outcome assessment, of early administration a single 4,500mg (or dose adjusted in moderate and severe impairment) VGB in 12 consecutive PASE subjects.

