### Screening

Screening will be done according to the inclusion and exclusion criteria and will be performed in multiple clinical areas, including the Emergency Department and ICU. The PI and co-investigators will be responsible for screening the EEG of eligible subjects for PASE development four times daily.

We will maintain a screening log to keep track of all eligible subjects, which will inform future decisions on inclusion/exclusion criteria in the subsequent study phases.

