### Blinding

The phase IIa feasibility study is open label. However, EEG recordings and Visual Field Perimetry will be centrally analyzed at the EEG and Visual Screening cores by an assessor that is blinded to the timing of VGB administration and drug levels. De-identified EEG recordings will be exported to Yale University for central analyses by [name], and de-identified Visual Field Perimetry studies will be exported to [name] at Tomas Jefferson University for central analyses in a blinded fashion. Clinical outcomes will be obtained by trained study personnel blinded to the timing of VGB administration and drug levels.

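### The claim that all endpoints are objective and assessed blind to VGB timing fails for several of them, and no blinded source is named for the PASE onset time behind the delivery outcomes

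*Combined protocol and SAP*

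**What the plan says.** Section 4 (Rationale for chosen outcomes) makes a claim without exceptions: "All the endpoints are objective and will be assessed by a blinded investigator to the timing of VGB administration". Section 6 (Trial design) calls the study an "open-label pilot, with blinded outcome assessment".

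The detail is narrower. Section 6 (Blinding) has EEG and perimetry read centrally "by an assessor that is blinded to the timing of VGB administration and drug levels", and has clinical outcomes collected by staff blinded to the same two things. Section 6 (Follow up) assigns the 6-month visits to blinded assessors.

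On delivery, primary outcome A says "We will primarily be looking at the ability to deliver VGB in PASE subjects" and sets a target of at least 80% of enrolled subjects within 48 h of PASE onset. The Rationale repeats the emphasis: "The explicit purpose of this feasibility study is to deliver the drug within 48 hours of PASE onset". A secondary outcome is the "proportion of enrolled subjects who received a VGB load within 12 and 24 hours of PASE onset".

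On finding PASE, section 6 (Screening) says: "The PI and co-investigators will be responsible for screening the EEG of eligible subjects for PASE development four times daily".

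**The concern.** An endpoint that consists of VGB timing cannot be assessed by someone who does not know VGB timing. The dose time is a recorded fact, so the judged part of the interval is PASE onset. For electrographic cases, the plan leaves that judgement by default to investigators who know the limit they are trying to meet.

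Two things are at stake. The first is the credibility of the 48 h proportion and of the 12 h and 24 h proportions, which are meant to inform ultra-early dosing in later phases. The second is how the exploratory efficacy measures will be read. Section 4 says they will guide the choice of endpoints for later phases, and a general blinding label credits some of them with protection they do not have.

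**Working it through.** The plan gives no figure to reproduce here, and section 12 omits power calculations. The check sets the general claim against each group of endpoints.

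1. **Delivery within 48 h (primary A) and within 12 and 24 h (secondary).** Each is dose time minus PASE onset, compared with a limit. Blinding to dose timing is impossible for the computed result. It is possible only for the onset time.
   - Electrographic cases: Screening gives detection to the investigators, and Blinding says the study is open label. No section says who fixes the onset time used in the endpoint, or whether it is the detection time or a look-back on the recording. Blinding does not say that the central EEG read supplies it.
   - Ictal-interictal continuum cases: section 5 (Inclusion criteria) sets onset at the antiseizure loading dose. That is a recorded time, but it follows from a treating-team decision.

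2. **Start of anesthetic wean, anesthetic duration, number of antiseizure drugs** (section 4, Exploratory outcomes). Blinded staff may record these, but unblinded clinicians generate them. Section 6 (Sedation) sets no sedation protocol, and section 6 (Monitoring for and treatment of seizures) allows discretionary departures from the treatment algorithm. The fixed infusion thresholds under Sedation partly standardise the anesthetic measures.

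3. **SF-36 and VFQ-25** are self-reports. **mRS, GOS-E and CPC** are ratings that involve judgement.

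4. **VGB, taurine and biomarker levels** are measured quantities. The word objective is fair for these.

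5. **What blinding to timing hides.** All 12 subjects receive VGB, so a rater blinded to timing and levels still knows that the subject was treated.

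Scale, taking all 12 subjects as the denominator:
- 0.80 × 12 = 9.6, so the target needs 10 subjects.
- 10/12 = 83.3% meets it and 9/12 = 75.0% does not. One subject is 1/12 = 8.3 points.

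Denominator: section 6 (Drug administration) makes a subject a screen failure if VGB is not given within exactly 48 h of electrographic onset, while outcome A counts enrolled subjects. As an illustration, suppose 9 of 12 are dosed in time. If the 3 late subjects stay in, the result is 9/12 = 75.0%. If they leave as screen failures, it is 9/9 = 100%. The documents do not say which applies.

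Illustration of onset error: four reviews a day, if evenly spaced, are 24/4 = 6 h apart. If onset were logged at detection, it would be up to 6 h late, and on average 3 h late if onset is uniform between reviews. Six hours is 6/12 = 50%, 6/24 = 25% and 6/48 = 12.5% of the three windows. Late logging shortens the apparent interval and so favours success. Both the spacing and logging at detection are assumptions.

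**The case against.** The strongest reply is about context. The sentence closes a paragraph on outcomes that reflect therapeutic effect, so it may never have been meant for delivery timing. That reading is plausible, but wean, anesthetic duration and drug count are exactly such outcomes, and they contradict it. The same paragraph itself warns that weaning practice may confound.

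Four stronger readings are tempting, and the documents do not support them.

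- **The investigators set onset knowing the dose time.** Screening comes before dosing, so no dose time exists when PASE is first detected. What they know at that point is the 48 h target. Nothing says onset is revised later, and nothing prevents it.
- **Onset is logged 3 to 6 h late.** The EEG is continuous and can be read back. Section 5 excludes onset before monitoring, which presupposes locating onset on the recording. Such a delay would also occur with a blinded screener, so it does not measure bias from lack of blinding.
- **Most endpoints lack the stated property.** No count shows this, and many endpoints are laboratory values or durations.
- **Only the central reads are blinded.** Blinding and Follow up also promise clinical assessors blinded to timing, and the plan never claims blinding to treatment. That narrower promise stands and should be kept.

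It also stands that the trial is a descriptive, single-arm feasibility study, that its open-label status is disclosed, and that the decision-driven and self-reported measures are exploratory.

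**Conclusion.** The general claim is wrong for several endpoints, including one of the three primary outcomes. The more consequential gap is that no one is assigned to fix electrographic PASE onset for the delivery proportions, although a blinded reader is already in the plan.

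The size is modest. No hypothesis test depends on it, and the documents show no actual bias. With 12 subjects in the denominator, one reclassified onset can move the result across the 80% target. If late-dosed subjects leave as screen failures, the 48 h proportion instead approaches 100% by construction, and the target tells the reader little. The change should be made before the delivery proportions are computed, but the point does not undermine the study.

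**What to change.** 1. **Onset and resolution times.** In primary outcome A, the secondary outcomes and Blinding, state that the 12, 24 and 48 h proportions and the time to PASE resolution use onset and resolution clock times set by the planned central EEG reader. The reader should work from recordings without drug annotations, and the times should be locked before they are merged with the dose time. Keep the local read for real-time eligibility and screen-failure status. Keep the antiseizure load time as onset for ictal-interictal continuum subjects.

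2. **Denominator.** Reconcile the screen-failure rule under Drug administration with the enrolled-subject denominator of outcome A, so that a later central read does not remove a dosed subject and late dosing is not excluded by construction.

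3. **Wording.** In Rationale for chosen outcomes and Trial design, drop the words all and objective. Limit the blinding claim to the central EEG and perimetry reads, and to clinical and follow-up assessments by personnel blinded to VGB timing and drug levels but not to treatment. Label wean, anesthetic duration and drug count as driven by open-label treatment decisions, and SF-36 and VFQ-25 as self-reports.

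The cost is protocol wording and two time fields in the central EEG report, with no extra reader. The downside is that a subject dosed in time by the local read may fall outside a window by the central read, so the delivery proportions may be slightly lower.

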## 5. Eligibility

### Inclusion criteria

After Institutional Review Board approval, individuals (and their legally authorized representative) meeting the following inclusion criteria will be approached: 1) 18 – 80 years of age, 2) non-traumatic CA (regardless of non-perfusing rhythm, etiology, or location of arrest) in whom the decision to treat unequivocal electrographic SE (as defined by the American Clinical Neurophysiology Society[69]: having generalized spike/sharp-wave discharges  $\geq 3\text{Hz}$  or any evolving pattern reaching  $> 4\text{Hz}$ , lasting  $\geq 10$  minutes, or comprising  $> 50\%$  of any hour of recording) has been made. The inclusion criteria will be expanded to include presumed electroclinical status epilepticus defined in this study as ictal -interictal continuum patterns of at least 1Hz as long as patient is treated with an antiseizure medication per the decision of the clinical treatment team. The time of onset for PASE in this setting will be the time of the loading dose of antiseizure medication. 3) requiring anesthetic infusion for any reason, 4) have reliable arterial access for frequent blood sampling and 5) established enteral access within 48h of PASE onset. The patient's legal authorized representative (LAR) will be identified with the clinical, research, and social work teams. The legal authorized representative will be approached to provide consent for participation in the study, during the patient's acute phase of ICU care after cardiac arrest, while the patient is in coma, undergoing continuous seizure monitoring. In the event COVID related restrictions do not allow for the LAR to come to the floor, we will proceed with remote consenting procedures with IRB approved scripts. Should the patient regain consciousness at any time during the 6-month study duration, they will individually be approached to provide their consent for continued participation in the research protocol. Further details on consent process are provided in Section 9.

### Exclusion criteria

Those with prior history of generalized epilepsy, history of gastrointestinal surgery within the last 21 days, and pregnant women will be excluded. In addition, those with PASE onset preceding initiation of EEG monitoring will be excluded.

### Note on inclusion and exclusion criteria

Outcomes following successful resuscitation in CA are multifactorial and depend on both the severity of systemic (myocardial, renal, and liver dysfunction) complications and the neurologic post-CA syndrome. Post-anoxic status epilepticus may occur following any type of CA, regardless of the location of its occurrence (out-of-hospital versus in-hospital) or the type of non-perfusing rhythm. Thus, we will include

all non-traumatic types of CA in this study. As with other ASDs, VGB may exacerbate certain types of primary epilepsy. Thus, we elect to exclude individuals with a history of primary generalized epilepsy. Lastly, as there is no parenteral formulation of VGB, enteral access is a requirement for participation in this study.

#### Note on inclusion window

The window from SE onset to drug delivery of 48 hours is very short, particularly when consent from a legally authorized representative is pursued in the acute setting and enteral access for drug delivery is required. To expedite the process, we will approach the legally authorized representatives of potential participants for consent as soon as interictal epileptiform activity is identified on EEG as these subjects are at high risk for subsequent PASE.

#### Exit from the study

Any subject (or legally authorized representative) is free to withdraw consent from the trial at any time. Doing so will constitute exit from the study. The reason for withdrawal will be collected and reported, including specifics as to which aspects of the trial from which consent and participation are withdrawn (e.g., attending follow-up visits, completing diagnostic testing, and allowing for inclusion of their data (including survival data) in a database or publication. According to federal requirements for FDA-regulated clinical trials, all data collected up to the point of subject withdrawal must be maintained in the database and included in subsequent analyses, as appropriate. Legal authorized representative and/or subjects will be informed of this requirement.

Discontinuation of the study intervention by the treating physician due to any adverse events, for example, does not constitute subject withdrawal from the study, and therefore, the subject will not exit the trial.

## 6. Trial design

Phase IIa: This is a feasibility, single center, open-label pilot, with blinded outcome assessment, of early administration a single 4,500mg (or dose adjusted in moderate and severe impairment) VGB in 12 consecutive PASE subjects.

#### General critical care

General critical care will be standardized as much as possible for all subjects across various treatment sites. Management of fluid homeostasis, hemodynamics, respiration, metabolic disturbances, and seizures will be according to local protocols and standard of care.

#### Sedation

There will not be a specifically-defined protocol for sedation analgesia for the purposes of the study. Documentation will be required on the indication for changes in the level of sedation. The bedside nurse will notify the study coordinator when titration of sedatives is required and inform clinical reasoning.

For purposes of data analysis for clinical outcomes, thresholds will be established for anesthetic infusions, whereby dosing below the threshold will be considered comfort/sedative dosing only, while dosing above the threshold will be considered as anti-seizure treatment, regardless of the indication. The anesthetic

